2.7 Interim Analyses

No interim analysis is planned for this trial. A Data Safety Monitoring Board (DSMB) will meet periodically to review the safety and scientific conduct of the study. At a minimum, the DSMB is to review adverse events and safety laboratory assessments after the first six subjects complete Day 5 of treatment, and again after the first 12 subjects complete Day 5 of treatment.

3. DATA HANDLING

3.1 Baseline and Study Visits

Study Day 1 will be the day of randomization.

The summary of hospitalization status will be based on the Study Day (derived relative to the day of randomization).

For the summary of inflammatory markers, Baseline will be the last assessment prior to dosing (SOC plus brequinar group) or last assessment on or prior to Study Day 1 (SOC group). Post-baseline timepoints will be based on the Study Day (derived relative to the day of randomization), where Day 15 includes a 4-day window (Study Day 11-19). If there are multiple results on the same day, the earliest result will be used.

For all other summaries, post-baseline timepoints will use the visit as recorded on the case report form, and Baseline will be the last non-missing value prior to randomization, including unscheduled assessments. Otherwise, unscheduled data will not be used in the analyses, but will be presented in the listings.

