1.2 Trial Design

This will be a phase 1a randomized, open label, multi-center study with approximately 24 subjects. All subjects will receive SOC per institutional guidelines for treatment of patients with COVID-19 infection. In addition to SOC, the brequinar group will receive brequinar 100 mg once daily for 5 days.

Subjects will have a Screening Visit followed as soon as possible with Study Day 1 (Day 1 may take place on the same day if entry criteria data are available). Subjects will be followed through Day 15, with mortality assessed via a phone call/other digital media acceptable to institution on Day 29.

Confidential Document

	CCB-CRISIS-01 Statistical Analysis Plan	Revision No. 1.0
	Document Date: 17-Dec-2020	Page 7 of 17

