2.5.3 Exploratory Efficacy Analyses

Changes from baseline will be summarized by treatment:

- Viral load (nasopharyngeal) (Days 3, 5, 7, and 15)
- Inflammatory markers (Days 3, 5, 7, and 15)
- DHO levels (Days 3, 5, 7, and 15)
- Brequinar concentration levels (Days 3, 5 and 7)

For inflammatory markers (including pro-inflammatory cytokines), results from both local and central laboratories will be combined, where the local test result will be normalized where necessary. (See [Section 3.2](#) for normalization method).

Viral culture results will be provided in data listings only.

Confidential Document

	CCB-CRISIS-01 Statistical Analysis Plan	Revision No. 1.0
	Document Date: 17-Dec-2020	Page 10 of 17

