a: P=Prior medication, C=Concomitant medication. A prior medication is any medication that started prior to date of randomization. A concomitant medication is any medication that either has a start date on or after date of randomization, or is ongoing on the date of randomization.								

Programming Note: Pharmacological Subgroup comes from ATC3. If ATC3 is not available, use ATC2.

Clear Creek Bio, Inc.: Protocol CCB-CRISIS-01

Listing 16.2.4.4

Listing of Prior and Concomitant Procedures by Treatment

Site-Subject	P: Procedure S: System Organ Class T: Preferred Term	Indication	Start Date	Stop Date (Ongoing)	Dose	Unit	Route	Prior/Con ^a
SOC + Brequinar								
xx-xxxx	P: xxxxxxxxxxxx S: xxxxxxxxxxxx T: xxxxxxxxxxxx	xxxxxxx	9999-99-99	9999-99-99	xxx	xxx	xxxxx	P
xx-xxxx	P: xxxxxxxxxxxx S: xxxxxxxxxxxx T: xxxxxxxxxxxx	xxxxxxx	9999-99-99	Ongoing	xxx	xxx	Other: xxxxx	P, C
	P: xxxxxxxxxxxx S: xxxxxxxxxxxx T: xxxxxxxxxxxx	xxxxxxx	9999-99-99	9999-99-99	xxx	xxx	xxxxx	C
SOC								
xx-xxxx	None							
xx-xxxx	P: xxxxxxxxxxxx S: xxxxxxxxxxxx T: xxxxxxxxxxxx	xxxxxxx	9999-99-99	Ongoing	xxx	Other: xxx	xxxxx	C
a: P=Prior procedure, C=Concomitant procedure. A prior procedure is any procedure that started prior to date of randomization. A concomitant procedure is any procedure that either has a start date on or after date of randomization, or is ongoing on the date of randomization.								

Clear Creek Bio, Inc.: Protocol CCB-CRISIS-01

Listing 16.2.5.1

Listing of Dosing Information (SOC + Brequinar Only)

Site-Subject	Day 1		Day 2		Day 3		Day 4		Day 5	
	Date of Dosing	Time of Dosing	Date of Dosing	Time of Dosing	Date of Dosing	Time of Dosing	Date of Dosing	Time of Dosing	Date of Dosing	Time of Dosing
xx-xxxx	9999-99-99	99:99	Not Done		9999-99-99	99:99	9999-99-99	99:99	9999-99-99	99:99
xx-xxxx	9999-99-99	99:99	9999-99-99	99:99	9999-99-99	99:99	9999-99-99	99:99	9999-99-99	99:99
xx-xxxx	9999-99-99	99:99	9999-99-99	99:99	9999-99-99	99:99	9999-99-99	99:99	Not Done	
xx-xxxx	Not Done		9999-99-99	99:99	9999-99-99	99:99	9999-99-99	99:99	9999-99-99	99:99

Clear Creek Bio, Inc.: Protocol CCB-CRISIS-01

Listing 16.2.5.2

Listing of PK/DHO Results by Treatment

Site-Subject	Visit	Not Done	Date Collected	Time Collected	PK Result (mcg/mL) ^a	DHO Result (ng/mL) ^a
SOC + Brequinar						
xx-xxxx	Day 1		9999-99-99	99:99	xxx	xxxx
	Day 3		9999-99-99	99:99	xxx	xxxx
	Day 5	Not Done				
	Day 7		9999-99-99	99:99	xxx	xxxx
	Day 15		9999-99-99	99:99	xxx	xxxx
SOC						

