Clear Creek Bio, Inc.: Protocol CCB-CRISIS-01
Listing 16.2.6.3
Listing of SARS-CoV-2 Viral Load and Viral Cultureunit by Treatment

Site-Subject	Visit	Not Done	Date Collected	Time Collected	Viral Load (copies/mL)	Viral Culture (unit)
SOC + Brequinar						
xx-xxxx	Day 1		9999-99-99	99:99		
	Day 3		9999-99-99	99:99		
	Day 5	Not Done				
	Day 7		9999-99-99	99:99		
	Day 15		9999-99-99	99:99		
SOC						
xx-xxxx	Day 1		9999-99-99	99:99		
	Day 3		9999-99-99	99:99		
	Day 5		9999-99-99	99:99		
	Day 7		9999-99-99	99:99		
	Day 15		9999-99-99	99:99		

Clear Creek Bio, Inc.: Protocol CCB-CRISIS-01
Listing 16.2.6.4
Listing of Hospitalization Log by Treatment

Site-Subject	Event Type	Event Date
SOC + Brequinar		
xx-xxxx	xxxxxxxxxxxxx	9999-99-99
xx-xxxx	xxxxxxxxxxxxx	9999-99-99
	Other: xxxxxxxxxxxxx	9999-99-99
	xxxxxxxxxxxxx	
SOC		
xx-xxxx	None	
xx-xxxx	Other: xxxxxxxxxxxxx	9999-99-99
	xxxxxxxxxxxxx	

Clear Creek Bio, Inc.: Protocol CCB-CRISIS-01

Listing 16.2.6.5

Listing of Survival Status by Treatment

Site-Subject	Visit	Date of Contact	Survival Status	Date of Death	Not Done, Comment
SOC + Brequinar					
xx-xxxx	Day 1 – Day 15		Alive		
	Day 29 Contact	9999-99-99	Alive		
xx-xxxx	Day 1 – Day 15		Patient Died	9999-99-99	
xx-xxxx	Day 1 – Day 15		Alive		
	Day 29 Contact				Not Done: xxxxxxxxxxxxxxxxx
SOC					
xx-xxxx	Day 1 – Day 15		Alive		
	Day 29 Contact	9999-99-99	Patient Died	9999-99-99	
xx-xxxx	Day 1 – Day 15		Alive		
	Day 29 Contact	9999-99-99	Alive		

Clear Creek Bio, Inc.: Protocol CCB-CRISIS-01

Listing 16.2.7.1

Listing of Adverse Events by Treatment

Site-Subject	Adverse Event Term/ System Organ Class/ Preferred Term	Onset Date and Time/ Resolution Date and Time	Continuing?	Outcome ^a	Severity	Causality	Action Taken with Study Treatment	Action Taken	Serious?
SOC + Brequinar									
xx-xxxx	xxxxxxx/ xxxxxxx / xxxxxxx*	9999-99-99T99:99/ 9999-99-99T99:99	Continuous	RG	Grade 2	Definite	Drug Interrupted	None	No
xx-xxxx	xxxxxxx/ xxxxxxx / xxxxxxx	9999-99-99T99:99/ 9999-99-99T99:99	Intermittent	RD	Grade 4	Probable	Drug Withdrawn	Treatment Prescribed	No
	xxxxxxx/ xxxxxxx / xxxxxxx	9999-99-99T99:99/ 9999-99-99T99:99	Continuous	RS	Grade 1	Possible	Unknown	Discontinued Study	No
SOC									
xx-xxxx	xxxxxxx/ xxxxxxx / xxxxxxx	9999-99-99T99:99/ 9999-99-99T99:99	Intermittent	NR	Grade 5	Unlikely	Not Applicable	Treatment Prescribed, Discontinued Study	Yes
	xxxxxxx/ xxxxxxx / xxxxxxx	9999-99-99T99:99/ 9999-99-99T99:99	Continuous	UN	Grade 3	Unrelated	Dose Not Changed	None	No

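### Section 3.1 sets inconsistent baseline rules: the inflammatory-marker cut-off differs by arm, and the rule for all other summaries drops Day 1 samples drawn after randomization but before dosing

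*SAP*

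**What the plan says.** Section 3.1 first fixes the time scale: "Study Day 1 will be the day of randomization". It then gives two baseline rules.

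- **Inflammatory markers.** Baseline is the "last assessment prior to dosing (SOC plus brequinar group) or last assessment on or prior to Study Day 1 (SOC group"). The same paragraph places post-baseline results by Study Day and ends: "If there are multiple results on the same day, the earliest result will be used".
- **All other summaries** (NEWS2, viral load, DHO, brequinar concentration, safety laboratory tests). "Baseline will be the last non-missing value prior to randomization, including unscheduled assessments". Post-baseline timepoints follow the visit on the case report form.

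Section 1.2 allows screening and Day 1 to coincide: "Day 1 may take place on the same day if entry criteria data are available". Section 2.5.3 makes change from baseline the exploratory summary: "Changes from baseline will be summarized by treatment". Section 3.3 plans no imputation.

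The shells for Listing 16.2.5.2, "Listing of PK/DHO Results by Treatment", and Listing 16.2.6.3, "Listing of SARS-CoV-2 Viral Load and Viral Cultureunit by Treatment", show Day 1 as the first row and no screening row. So do the NEWS2 shell (16.2.6.1) and the chemistry shell (16.2.8.1.1). The corresponding summary tables go from Baseline to Day 3, or to Day 2 for laboratory tests.

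**The concern.** A change from baseline compared by arm needs the same time origin in both arms. The marker rule does not secure that. It stops the brequinar baseline at first dose but leaves the SOC baseline open until the end of the randomization day.

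The general rule has the opposite problem. It treats the arms alike, but it rejects a sample taken after randomization and before dosing, which the marker rule accepts. The SAP thus gives two answers on whether such a sample is a valid untreated baseline.

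At stake are the change columns for the exploratory measures and NEWS2, and for the safety laboratory parameters, which serve the primary objective. With about 16 brequinar and 8 SOC subjects, a few missing baselines would be visible.

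**Working it through.** The SAP states no figure on this point and has no sample-size calculation to reproduce. The one piece of arithmetic available agrees with section 1.2.1: 24 subjects at 1:2 give 24/3 = 8 SOC and 48/3 = 16 brequinar.

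**Step 1: the rules side by side.**

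| Sample | Marker rule, brequinar | Marker rule, SOC | General rule, both arms |
|---|---|---|---|
| Before randomization | eligible | eligible | eligible |
| Day 1, after randomization, before first dose | eligible | no dose in this arm; eligible all day | not eligible |
| Day 1, after first dose | not eligible | no dose in this arm; eligible all day | not eligible |
| After Day 1, before a delayed first dose | eligible | not eligible | not eligible |

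The last row is not fanciful: the dosing shell (Listing 16.2.5.1) includes an example subject with no Day 1 dose and a first dose on Day 2.

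**Step 2: what a later SOC baseline does.** Assume, since the SAP gives neither, that a marker falls by a share r per day in both arms and that the SOC baseline is drawn g hours later. The ratio of SOC to brequinar baseline is k = (1 − r)^(g/24).

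| r per day | g = 6 h | g = 12 h | g = 24 h |
|---|---|---|---|
| 0% | 1.000 | 1.000 | 1.000 |
| 10% | 0.974 | 0.949 | 0.900 |
| 20% | 0.946 | 0.894 | 0.800 |
| 30% | 0.915 | 0.837 | 0.700 |

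Let the brequinar baseline be B and let both arms have the same later value V. The changes are V − B and V − kB, which differ by −(1 − k)B with no drug effect. At 20% per day and 12 hours that is 1 − 0.894 = 0.106, or 10.6% of B, in the direction of a larger fall on brequinar. For a rising marker, or a brequinar baseline later than the SOC one, the sign reverses. With no gap or no trend it is zero.

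**Step 3: lost change values under the general rule.** Let p be the share of subjects whose Day 1 sample precedes randomization. Assume that no screening or unscheduled value exists for the measure and that subjects are independent. The expected numbers with a change value are 16p and 8p. The chances that an arm has none are (1 − p)^16 and (1 − p)^8.

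| p | Expected, brequinar / SOC | Chance of none, brequinar / SOC |
|---|---|---|
| 0 | 0 / 0 | 100% / 100% |
| 0.10 | 1.6 / 0.8 | 18.5% / 43.1% |
| 0.25 | 4 / 2 | 1.0% / 10.0% |
| 0.50 | 8 / 4 | <0.1% / 0.4% |
| 1 | 16 / 8 | 0% / 0% |

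The SAP does not give p, so this table shows sensitivity and is not a forecast.

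**Step 4: the same-day rule.** Take an SOC subject with two marker results on Day 1. If the earliest-result sentence covers only post-baseline days, baseline is the later result. If it also covers baseline, it is the earlier one. The text supports either reading, so two programmers could produce different baselines.

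**The case against.** The case on the other side has real weight.

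- **Dosing time.** SOC subjects have no dosing time, so an identical rule tied to dosing is impossible, and Study Day 1 is a natural substitute. With a single Day 1 draw before dosing, the two marker rules give comparable baselines. This stands, and it means that the asymmetry need not produce a bias. It does not remove the asymmetry where SOC has later Day 1 draws.
- **Mock shells.** Shell rows are placeholders and not a sampling schedule. The timing of Day 1 samples may well be in the protocol, which is not shown. This also stands: the shells suggest that Day 1 is the first DHO and viral-load sample but do not prove it.
- **Last against earliest.** The earliest-result sentence directly follows the one on post-baseline timepoints. If it did reach baseline, it would shrink the gap in Step 2. The point is therefore an ambiguity of scope and not a contradiction, and the two effects cannot both be counted in full.
- **Consequence.** No hypothesis test is planned, and the markers, DHO and viral load are exploratory. The tables also show raw values by visit, so a missing baseline costs only the change column.

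A reader might infer that the general rule excludes all Day 1 samples taken before dosing. It does not: one drawn before randomization qualifies, as does a same-day screening value or an earlier unscheduled one. Reading the rule by calendar date would exclude every Day 1 sample. However, the rule does not mention the date, whereas the medication rule in section 3.2 does, and Listing 16.2.2 records the time of randomization.

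**Conclusion.** The inconsistency holds on the text of section 3.1. Followed literally, the marker rule can give the arms different time origins, and the general rule can discard usable untreated values that the marker rule would accept. The scope of the same-day rule needs a sentence.

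The size is not known. The marker distortion ranges from nil to a baseline ratio of 0.70 under the assumptions above, and its direction depends on the marker's trend and on which arm is sampled later. The number of subjects without a change value lies between 0 and 24, depending on when Day 1 samples are drawn and whether earlier values exist.

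Two stronger conclusions are tempting: that the marker comparison is biased in a known direction, and that the DHO and viral-load change tables will be empty. The document supports neither, because it gives no sampling times or marker trends. Both are risks that clearer wording would largely remove.

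**What to change.** Replace the two rules in section 3.1 with one for both arms and all parameters:

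1. Baseline is the latest non-missing value taken at or before the date and time of randomization.
2. If there is none, use the earliest Day 1 value in either arm. In the brequinar arm it must also precede the first dose.
3. Apart from that fallback, the earliest-result rule applies to post-baseline days only.
4. Flag in the listings each subject whose baseline comes from the fallback.

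The cost is SAP wording and minor programming. Randomization time is already in Listing 16.2.2, dosing times are in 16.2.5.1, and collection times are in 16.2.5.2, 16.2.6.1, 16.2.6.2, 16.2.6.3 and 16.2.8.1.1, so no new data are needed. The downside is a small remaining difference between arms for fallback subjects, because only the brequinar arm has a first dose to cut at. Taking the earliest Day 1 value limits this, and the flag shows how many subjects it concerns.

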1.3 Trial Objectives

1.3.1 Primary Objectives

The primary objective of this study is to determine the safety and tolerability of SOC and SOC plus brequinar in hospitalized COVID-19 subjects.

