2.6 Safety Analyses

Adverse Events

An overall summary of treatment-emergent adverse events (TEAEs) will be presented by treatment and total, including the total number of events, frequency counts and percentages for:

- Any TEAE
- Treatment-related TEAEs
- CTCAE Grade 3 or above TEAEs
- TEAEs leading to drug withdrawn
- TEAEs leading to study discontinuation
- Serious TEAEs
- Fatal TEAEs
- TEAEs of interest

The incidence of TEAEs by treatment and total will be tabulated by MedDRA system organ class and preferred term for:

- All TEAEs
- Treatment-related TEAEs
- TEAEs by severity
- TEAEs leading to study discontinuation
- Serious TEAEs
- TEAEs of interest

AEs will be considered treatment-emergent if the onset date is on or after the day of randomization. “Drug related” will include ‘Definite’, ‘Probable’ and ‘Possible’ relationship to drug as determined by the Investigator.

Safety Laboratory Assessments

Safety laboratory tests (Chemistry and Hematology) will be performed throughout the study. Laboratory parameters of interest (AST, ALT, ALP, Total Bilirubin, Creatinine, Hemoglobin, WBC, Absolute Neutrophils, Absolute Lymphocytes and Platelets) will be summarized for changes from baseline.

Confidential Document

	CCB-CRISIS-01 Statistical Analysis Plan	Revision No. 1.0
	Document Date: 17-Dec-2020	Page 11 of 17

NCI CTCAE grades will be derived for the lab parameters included in [Appendix 1](#) and presented in data listings. Separate listings of Grade 3 or 4 values will also be provided.

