Listing 16.2.6.3	Listing of SARS-CoV-2 Viral Load and Viral Culture by Treatment
Listing 16.2.6.4	Listing of Hospitalization Log by Treatment
Listing 16.2.6.5	Listing of Survival Status by Treatment
Listing 16.2.7.1	Listing of Adverse Events by Treatment
Listing 16.2.7.2	Listing of Related Adverse Events by Treatment
Listing 16.2.7.3	Listing of Serious Adverse Events by Treatment
Listing 16.2.7.4	Listing of Grade 3 or 4 Adverse Events by Treatment
Listing 16.2.8.1.1	Listing of Chemistry Laboratory Tests by Treatment
Listing 16.2.8.1.2	Listing of Grade 3 or 4 Chemistry Laboratory Tests by Parameter and Treatment
Listing 16.2.8.2.1	Listing of Hematology Laboratory Tests by Treatment
Listing 16.2.8.2.2	Listing of Grade 3 or 4 Hematology Laboratory Tests by Parameter and Treatment
Listing 16.2.8.3	Listing of Urinalysis Laboratory Tests by Treatment

Conventions:

- For categorical data:
 - Percents are displayed with one decimal
 - When displaying counts and percents, the percent is contained within parentheses and does not include the “%” symbol
 - If the count is zero, no percent is displayed
 - If missing data occurs, a “Missing” row will be added to the summary table. The count of missing will be presented (no percent). The percentages for remaining rows will be based on the number of non-missing responses (i.e., the denominator does not include the missing counts)
- For continuous data, rounding will be based on the following conventions unless otherwise specified
 - Min and Max displayed to the same number of decimals as the original data
 - Mean, Median, and other percentiles displayed to 1 more decimal than the original data
 - SE and CIs displayed to 2 more decimals than the original data

Clear Creek Bio, Inc.: Protocol CCB-CRISIS-01

Table 14.1.1

Summary of Populations by Site and Treatment

	SOC + Brequinar n (%)	SOC n (%)
Overall		
Randomized	xx	xx
Modified Intent-to-Treat ^a	xx (xx.x)	xx (xx.x)
Site xx		
Randomized	xx	xx
Modified Intent-to-Treat ^a	xx (xx.x)	xx (xx.x)
a: Modified Intent-to-Treat (mITT) population includes all randomized subjects who had at least one post-randomization assessment, and who received at least one dose of study medication if randomized to SOC + Brequinar group. Source: Listing 16.X.X.X		

Clear Creek Bio, Inc.: Protocol CCB-CRISIS-01
 Table 14.1.2
 Summary of Subject Disposition by Site and Treatment
 Modified Intent-to-Treat Population

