Summary of Change from Baseline in Laboratory Parameters of Special Interest by Treatment and Visit
 Modified Intent-to-Treat Population

Parameter Visit	SOC + Brequinar (N=xx)		SOC (N=xx)	
	Visit	Change from Baseline	Visit	Change from Baseline
Parameter 1 (unit)				
Baseline				
n	xx		xx	
Mean (SE)	xx.x (xx.xx)		xx.x (xx.xx)	
Median	xx.x		xx.x	
Q1, Q3	xx.x, xx.x		xx.x, xx.x	
Min, Max	xx, xx		xx, xx	
Day 2				
n	xx	xx	xx	xx
Mean (SE)	xx.x (xx.xx)	xx.x (xx.xx)	xx.x (xx.xx)	xx.x (xx.xx)
Median	xx.x	xx.x	xx.x	xx.x
Q1, Q3	xx.x, xx.x	xx.x, xx.x	xx.x, xx.x	xx.x, xx.x
Min, Max	xx, xx	xx, xx	xx, xx	xx, xx
Day 3				
n	xx	xx	xx	xx
Mean (SE)	xx.x (xx.xx)	xx.x (xx.xx)	xx.x (xx.xx)	xx.x (xx.xx)
Median	xx.x	xx.x	xx.x	xx.x
Q1, Q3	xx.x, xx.x	xx.x, xx.x	xx.x, xx.x	xx.x, xx.x
Min, Max	xx, xx	xx, xx	xx, xx	xx, xx
etc.				
Parameter 2 (unit)				
Baseline				
Source: Listing 16.x.x.x				

Programming note: Include selected lab parameters: AST, ALT, ALP, Total Bilirubin, Creatinine, Hemoglobin, WBC, Absolute Neutrophils, Absolute

Clear Creek Bio, Inc.: Protocol CCB-CRISIS-01
Listing 16.2.1
Listing of End of Study Status by Treatment

Site-Subject	Date of Last Contact	Did the patient complete the study?	Primary Reason Did Not Complete	Comments
SOC + Brequinar				
xx-xxxx	9999-99-99	Yes		
xx-xxxx	9999-99-99	Yes		XXXXXXXXXXXXXXXX
SOC				
xx-xxxx	9999-99-99	No	XXXXXXXXXXXXXXXX	XXXXXXXXXXXXXXXX
xx-xxxx	9999-99-99	Yes		

Clear Creek Bio, Inc.: Protocol CCB-CRISIS-01

Listing 16.2.2

Listing of Inclusion/Exclusion Criteria and Randomization

Site-Subject	Does the subject meet all the Inclusion/Exclusion criteria?	Criterion Not Met	Comment / Explain Reason for Ineligibility	Date of Randomization	Time of Randomization	Treatment Assignment	ICU Level of Care at Randomization
xx-xxxx	Yes			9999-99-99	99:99	SOC	No
xx-xxxx	No	Exclusion 2 Inclusion 1	xxxxxxxxxx xxxxxxxxxx				Yes
xx-xxxx	Yes			9999-99-99	99:99	SOC + Brequinar	No
xx-xxxx	No	Inclusion 3	xxxxxxxxxx				No
xx-xxxx	Yes			9999-99-99	99:99	SOC + Brequinar	Yes
xx-xxxx	Yes			9999-99-99	99:99	SOC	No

Clear Creek Bio, Inc.: Protocol CCB-CRISIS-01

Listing 16.2.3

Listing of Informed Consent and Study Populations by Treatment

Site-Subject	Date of Informed Consent	Time of Informed Consent	Modified Intent-to-Treat Population ^a
SOC + Brequinar			
xx-xxxx	9999-99-99	99:99	Yes
xx-xxxx	9999-99-99	99:99	Yes
xx-xxxx	9999-99-99	99:99	Yes
SOC			
xx-xxxx	9999-99-99	99:99	xxx
xx-xxxx	9999-99-99	99:99	xxx
xx-xxxx	9999-99-99	99:99	xxx

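### No by-arm table shows each subject's worst post-baseline laboratory grade, because post-baseline unscheduled results are excluded and CTCAE laboratory grades are only listed

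*SAP*

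**What the plan says.** SAP Section 1.3.1 sets the aim: "The primary objective of this study is to determine the safety and tolerability of SOC and SOC plus brequinar in hospitalized COVID-19 subjects".

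SAP Section 2.6 names ten laboratory parameters of interest, ending with "Absolute Neutrophils, Absolute Lymphocytes and Platelets) will be summarized for changes from baseline". In the same section, CTCAE grades are to be derived for the Appendix 1 parameters "and presented in data listings. Separate listings of Grade 3 or 4 values will also be provided".

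SAP Section 3.1 has a paragraph for all summaries other than hospitalization status and inflammatory markers, so it governs the safety laboratory summary. Post-baseline timepoints there follow the visit recorded on the case report form, and "Baseline will be the last non-missing value prior to randomization, including unscheduled assessments". The next sentence is the exclusion: "Otherwise, unscheduled data will not be used in the analyses, but will be presented in the listings".

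The index of proposed outputs has a single laboratory safety table, Table 14.3.2: "Summary of Change from Baseline in Laboratory Parameters of Special Interest by Treatment and Visit". The Grade 3 or 4 results go to Listing 16.2.8.1.2, "Listing of Grade 3 or 4 Chemistry Laboratory Tests by Parameter and Treatment", and to Listing 16.2.8.2.2, its hematology counterpart.

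**The concern.** Two separate choices combine. The first removes unscheduled post-baseline results from the summaries. Such tests are often ordered because something looks wrong, so they may hold a subject's most extreme value. The second derives a toxicity grade for each result but never tabulates it. A report written exactly to this plan could describe laboratory safety by arm only through by-visit distributions of ten parameters. The question a safety reader asks first is how many subjects in each arm reached Grade 3 or higher, and from what baseline grade. That question would have no prespecified table.

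The SAP takes the worst case elsewhere. Table 14.3.1.7 counts each adverse event term at its maximum severity, and Section 3.2 takes the worst hospitalization status on a given day. Laboratory grades get no such summary.

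**Working it through.** The SAP states no figure that can be reproduced on this point. The check traces the rules through the outputs.

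1. **Parameters.** Appendix 1 grades 15: albumin, ALP, ALT, AST, total bilirubin, calcium, creatinine, glucose, potassium, sodium, lymphocytes, neutrophils, hemoglobin, platelets and WBC. Section 2.6 and Table 14.3.2 cover 10. The difference, 15 − 10 = 5 (albumin, calcium, glucose, potassium, sodium), is graded but is in no laboratory table.

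2. **Outputs.** Counting the index of tables and listings:

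| Output type | Number |
|---|---|
| Laboratory safety tables, any kind | 1 (Table 14.3.2) |
| Tables of laboratory CTCAE grade, worst grade, shift or Grade 3–4 incidence | 0 |
| Dedicated listings of Grade 3 or 4 laboratory values | 2 |

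3. **Where the exclusion bites.** The mock chemistry listing (16.2.8.1.1) shows Days 1 to 7 and then Day 15. If that is the draw schedule, Days 8 to 14 have no planned draw: 7 of the 14 days from Day 2 to Day 15. A value seen only on an unscheduled draw in that interval would reach the listings but not Table 14.3.2. The SAP gives no rate of unscheduled testing, so how often this happens cannot be calculated.

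4. **Whether Min and Max stand in for a grade.** Table 14.3.2 prints both, by arm and visit, for the value and for the change. For ALP, ALT, AST, bilirubin and creatinine, Appendix 1 grades on multiples of ULN. Take ALT, where Grade 3 starts above 5 × ULN, and two laboratories with ULN_a < ULN_b. Any value between 5 × ULN_a and 5 × ULN_b is Grade 3 at the first and below Grade 3 at the second. The listing shell records a laboratory name (with an Other option) and a reference range for each result, so more than one range is expected. A raw maximum therefore need not identify the grade. It also cannot give a count: two affected subjects at one visit yield one maximum, and one subject affected at three visits yields three.

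5. **What a by-arm count would look like.** Section 1.2.1 plans about 24 × 2/3 = 16 subjects on SOC plus brequinar and 24 × 1/3 = 8 on SOC. One subject at Grade 3 or 4 would be 1/16 = 6.3% (exact 95% CI 0.2 to 30.2%) or 1/8 = 12.5% (0.3 to 52.7%). The chance of at least one such subject is 1 − (1 − p)^n. For assumed true rates p of 5%, 10% and 20% it is 56%, 81% and 97% with n = 16, and 34%, 57% and 83% with n = 8. These rates are assumptions, used only to show that the table would probably not be empty.

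**The case against.** The strongest reply is that nearly all of this information is already shown for each arm, and much of it stands.

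- **Grade 3 or 4 listings.** They are organised by parameter and treatment and include unscheduled results. With about 16 and 8 subjects a reader can count by hand. This is true, but the denominator, the treatment of subjects already abnormal at entry, and repeated values are then left to whoever counts.
- **Min and Max in Table 14.3.2.** An extreme value at a scheduled visit is visible for the ten parameters. That stands, within the limits in step 4 of the working.
- **Adverse event tables.** A laboratory abnormality reported as an adverse event enters Tables 14.3.1.1 and 14.3.1.7 with its grade, whatever the visit. That stands too. The SAP does not say when a value becomes an adverse event. This is commonly a protocol matter and is not faulted here. In an open-label trial, however, that judgement could differ by arm, whereas derived grades do not depend on it.
- **DSMB.** Section 2.7 has it review safety laboratory assessments during the trial. That is oversight, not a reported analysis.

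A reader might infer that unscheduled results are barred from every summary. Section 3.1 does not say so: they may serve as Baseline, and inflammatory markers are placed by Study Day under a separate rule. A reader might also infer that the worst laboratory toxicity appears in no by-arm table. The second and third items above show that this goes too far.

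**Conclusion.** The point holds in a limited form. The SAP gives no by-arm table of worst post-baseline laboratory grade or of the number of subjects with Grade 3 or 4 values, although safety is the primary objective and the grades are derived anyway. The other outputs show part of this but give no by-arm subject count based on derived grades.

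It would be wrong to conclude that the plan hides toxicity or biases a Grade 3–4 rate. No such laboratory rate is planned, so none can be biased, and every value remains in the listings. How many affected subjects would be missing from Table 14.3.2 cannot be estimated from this document. It depends on how often an unscheduled draw catches a peak that scheduled draws miss, and the SAP gives nothing on that.

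This is a cheap improvement in how the primary objective is summarised. The output counts rest on the SAP text and its index. The Day 8 to 14 gap rests on a mock listing.

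**What to change.** In Section 3.1, limit the exclusion of unscheduled data to by-visit summaries.

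In Section 2.6 and the table index, add one by-arm table of baseline CTCAE grade against worst post-baseline grade, using all scheduled and unscheduled results, with n (%) at Grade 3 or higher. State the denominator, for example subjects with at least one post-baseline result for that parameter. Cover all 15 Appendix 1 parameters.

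Three details need a rule:

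- **Direction.** Calcium, glucose, potassium, sodium, lymphocytes, hemoglobin and WBC are graded for both high and low values and need separate rows. Hemoglobin has two rows for high values and neutrophils two for low values, so say which row is used.
- **Clinical review.** Appendix 1 marks some grades as needing clinical review: Grade 4 for albumin, low hemoglobin, high WBC and one of the neutrophil rows, and Grade 1 for low potassium. Flag these in the table, since the number alone does not settle them.
- **Testing frequency.** Subjects tested more often have more chances to show a high grade, and in an open-label trial this may differ by arm. Footnote the number of tests per arm.

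The cost is one changed sentence, one added sentence and one table from grades already derived, plus these rules.
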